### 9.4.2 Cardiovascular Statistical Methodology

Observed values, as well as change from baseline, for all cardiovascular parameters (including peak hourly mean SBP and mean hourly SBP values), will be listed and summarized by treatment using descriptive statistics. Mean hourly SBP values will be plotted over time, together with changes from baseline. In addition, mean hourly SBP and peak hourly mean SBP values will be plotted against plasma concentrations of lasmiditan to explore the relationship between PK and cardiovascular effects.

As a primary analysis, changes from baseline in peak hourly mean values of SBP will be analyzed to test whether each dose of lasmiditan (100 mg, 200 mg) is non-inferior to placebo, assuming a non-inferiority margin of 10 mmHg. Specifically, these changes from baseline will be analyzed to test the null hypothesis that the difference in mean baseline change between lasmiditan at each dose and placebo is at least 10 mmHg versus the alternative hypothesis that this difference is less than 10 mmHg.

A linear mixed-effects model with baseline as a covariate, fixed effects for treatment, period (1, 2, or 3), and treatment sequence, and a random effect for subject will be used to test the hypotheses at a 1-sided significance level of 0.05. Least squares (LS) means and treatment differences (lasmiditan 200 mg – placebo, lasmiditan 100 mg – placebo) will be calculated and presented with their corresponding 95% confidence intervals (CIs).

An example of the SAS code that will be used is as follows:

```
proc mixed data=xxx;
  class trtmnt period sequence subject;
  model cardiochg = baseline trtmnt period sequence / alpha=0.05 cl ddfm=kr;
  random subject;
  lsmeans trtmnt;
  lsestimate trtmnt 'Ltn100 - Placebo' 1 0 -1 / lower testvalue=10 cl alpha=0.05;
  lsestimate trtmnt 'Ltn200 - Placebo' 0 1 -1 / lower testvalue=10 cl alpha=0.05;
run;
```

where cardiochg is the change from baseline in peak hourly mean values of SBP, trtmnt is the treatment, and seq is the treatment sequence.

The following gatekeeping procedure will be used to adjust for multiplicity when conducting the hypothesis tests. The null hypothesis that the difference in mean baseline change between lasmiditan 100 mg and placebo is at least 10 mmHg will first be tested against the alternative hypothesis that this difference is less than 10 mmHg. If the p-value for this test is less than 0.05, then there is significant evidence that lasmiditan 100 mg is non-inferior to placebo and these hypotheses will be re-tested using lasmiditan 200 mg. Otherwise, if the p-value is at least 0.05, then there is no significant evidence that lasmiditan 100 mg is non-inferior to placebo, in which case the null and alternative hypotheses will not be re-tested using lasmiditan 200 mg.

A sensitivity analysis will be performed on subjects who complete all 3 dosing periods. In addition, sensitivity analyses will be conducted where baseline value is the mean SBP value during the 1 hour pre-dose for each period. These analyses will be performed separately on subjects who complete at least 1 dosing period and on subjects who complete all 3 dosing periods. The same mixed-effects model as that was used in the primary analysis will be implemented.

A repeated measures analysis will also be conducted in which changes from baseline in hourly mean values of SBP will be analyzed to test whether each dose of lasmiditan (100 mg, 200 mg) is non-inferior to placebo at each time point (hour), assuming a non-inferiority margin of 10 mmHg. A repeated measures linear mixed-effects model with baseline as a covariate, fixed effects for time point, treatment, period, treatment sequence, and the treatment by time point interaction, and a random effect for subject will be used to conduct the tests at a 1-sided significance level of 0.05. An unstructured covariance structure will be applied. If the model fails to converge, alternative structures shall be examined using Akaike's criteria. At each time point, LS means and treatment differences (lasmiditan 200 mg – placebo, lasmiditan 100 mg - placebo) will be calculated and presented with their corresponding 95% CIs, from which non-inferiority of lasmiditan (100 mg, 200 mg) to placebo will be determined if the upper confidence limit is less than 10 mmHg.

An example of the SAS code that will be used is as follows:

```
proc mixed data=xxx;
  class trtmnt time period seq subject;
  model cardiochg = base time trtmnt period seq trtmnt*time / alpha=0.05 cl ddfm=kr;
  repeated time / type=un subject=subject;
  random subject;
  lsmeans trtmnt*time / alpha=0.05 cl pdiff=controll('reftrt');
run;
```

where cardiochg is the change from baseline in hourly mean values of SBP, trtmnt is the treatment, seq is the treatment sequence, and reftrt is the reference treatment of the comparison.

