#### 3.2. Background

Across the completed Phase 1, 2, and 3 clinical studies, doses of 0.1 to 400 mg of lasmiditan were evaluated in healthy subjects or patients with migraine. Compared with placebo, the most frequently reported lasmiditan treatment-emergent adverse events (TEAEs) included dizziness, paresthesia, somnolence, fatigue, lethargy, and nausea. A majority of these TEAEs were mild or moderate in severity and none led to subject withdrawal. One patient experienced a serious adverse event (SAE) of dizziness that was moderate in severity (lasmiditan 200 mg) (Färkkilä et al. 2012).

In the thorough QT study in healthy subjects, no clinically significant changes in BP, heart rate, or 12-lead electrocardiogram (ECG) were observed at the 100- or 400-mg single-dose levels.

In healthy subjects, peak plasma concentrations of lasmiditan were observed approximately 1.5 to 2.5 hours after a single oral dose ranging from 25 to 400 mg, and the geometric mean terminal half-life was approximately 4 hours. Lasmiditan exhibited dose-linear PK.

Co-administration of lasmiditan with a high-fat diet led to a delay in median time of maximum observed drug concentration (tmax) value by approximately 1 hour and a modest (~20%) increase in lasmiditan maximum observed drug concentration (Cmax), and area under the concentration versus time curve (AUC) values, relative to that under fasted conditions.

Following oral dosing with lasmiditan, up to 11 metabolites were detected in human plasma and urine, including 3 major metabolites (M7, M8, and M18). These metabolites lacked significant pharmacological activity at the 5 HT1F receptor and were generally considered to be pharmacologically inactive. The relative proportions of metabolites to intact lasmiditan remained reasonably constant throughout the oral dose range studied and their PK was approximately linear. The half-life of the metabolites ranged from ~4.5 to 21 hours.

Preliminary PK results from Study LAHA demonstrated that in elderly subjects, exposure to lasmiditan as measured by AUC from zero to infinity was 26% (90% confidence intervals (CIs) 1.03, 1.55) higher than in young subjects following dosing with 200 mg lasmiditan. There was no statistically significant difference in exposure to lasmiditan based on Cmax. The tmax of lasmiditan was similar between age groups. The geometric mean t1/2 was 5.46 and 4.10 hours in elderly and young subjects, respectively.

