## 7. Treatment

### 7.1. Treatment Administered

Investigational products used in this study are shown in [Table 7.1](#).

Tablets of lasmiditan and/or placebo will be administered orally in the fasted state with approximately 240 mL of room temperature water in the morning of Days 1, 3, and 5, while subjects are in a sitting position. Subjects will not be allowed to lie supine for 2 hours after dosing, unless clinically indicated or for study procedures.

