#### **9.4.2.1. Ambulatory Blood Pressure Monitoring**

For each subject, ABPM will be performed according to the Schedule of Activities (Section 2).

Site investigative personnel should be trained on the correct positioning of the ABPM monitor, use of correct cuff size, and monitor calibration prior to the start of the study. Subjects should be trained on the ABPM device on the evening of Day -1 to maximize the collection of valid measurements, and to alleviate any concerns about inconvenience due to the continuous 24-hour monitoring.

The ABPM device should be attached to the subject's nondominant arm and will record ambulatory BP and PR every 20 minutes during awake hours (e.g. 0700 hours to 2200 hours) and every 30 minutes throughout the night (2200 hours to 0700 hours). On Days 1, 3, and 5 when dosing occurs, the BP and PR recording will be initiated approximately 2 hours prior to the planned dosing time and will continue for approximately 26 hours. Subjects will be encouraged to keep the same routine without strenuous activity during the ABPM recording days.

The ABPM device should be removed from each subject prior to their discharge from the CRU.

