#### **9.5.1. Bioanalysis**

Samples will be analyzed at a laboratory approved by the sponsor and stored at a facility designated by the sponsor.

Concentrations of lasmiditan will be assayed using a validated liquid chromatography with tandem mass spectrometry method. Analyses of samples collected from subjects who received placebo are not planned.

Bioanalytical samples collected to measure investigational product concentrations will be retained for a maximum of 1 year following last subject visit for the study.

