#### **10.3.4. Pharmacokinetic/Pharmacodynamic Analyses**

The relationship between PK and cardiovascular effects will be explored initially in a graphical manner. Additional modeling approaches or graphical analyses may be used, if warranted.

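### The hourly SBP-versus-concentration plot has no time-matched placebo correction, so the daily blood pressure rhythm can bias the apparent exposure-response by a small to moderate amount in either direction.

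*SAP*

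**What the plan says.** On exposure and response, SAP section 9.4.2 states that "mean hourly SBP and peak hourly mean SBP values will be plotted against plasma concentrations of lasmiditan to explore the relationship". The sentence just before it, on the time-course figures, reads "Mean hourly SBP values will be plotted over time, together with changes from baseline". Changes from baseline are therefore named for the time plots, but neither they nor a placebo difference is named for the concentration plots.

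Protocol section 10.3.4 sets the status of this work: "The relationship between PK and cardiovascular effects will be explored initially in a graphical manner", followed by "Additional modeling approaches or graphical analyses may be used, if warranted".

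Four other provisions matter:

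- Tablets are given "in the morning of Days 1, 3, and 5" (Protocol 7.1), so all three periods share the same part of the clock.
- ABPM starts about 2 hours before dosing and runs about 26 hours, including the night (Protocol 9.4.2.1).
- PK samples in the Schedule of Activities fall at 0.5, 1, 1.5, 2, 2.5, 3, 4, 6, 8, 12, 24 and 36 h after dosing. None lies between 12 and 24 h.
- For placebo, Protocol 9.5.1 says: "Analyses of samples collected from subjects who received placebo are not planned". The SAP text gives no rule for how placebo periods enter the plots.

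**The concern.** With morning dosing, a high concentration means late morning and a low one means evening or the next morning. Blood pressure also has a daily rhythm. A plot of one against the other therefore mixes any drug effect with time of day. Subjects' blood pressure levels also differ, and that spread hides a modest effect.

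The study follows up a transient SBP rise seen 60 to 90 minutes after 200 mg in elderly subjects, so readers will look to this figure to see whether SBP tracks concentration. The crossover gives each completer a placebo day at the same clock hours, and the figure as specified does not use it. The risk is a misleading exploratory figure, and possibly a poor choice of follow-on modelling. No confirmatory conclusion is at stake.

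**Working it through.** **The plan's own figure.** The documents give no figure for these plots. The only design figure is at least 90% power with 30 completers (Protocol 10.1). It reproduces. Reading 6.0 mmHg as the within-subject SD, the standard error is 6 × √2 / √30 = 1.549. Then (10 − 5) / 1.549 − 1.645 = 1.582, which gives 94.3%. Reading 6.0 as the SD of the paired difference gives 99.8%. Nothing below changes this.

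**Why the choice of variable matters.** Write hourly SBP for subject i, period j and hour h as

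Y = subject level + period level + f(clock hour) + g(concentration) + noise.

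- *Uncorrected SBP:* all terms remain.
- *Change from the pre-dose baseline:* the subject and period levels cancel. f(hour) − f(pre-dose) remains, so the clock artefact is untouched.
- *Change on the active day minus change on the placebo day at the same hour:* f cancels, leaving g(concentration) plus noise. This needs similar dosing times across periods. The Schedule of Activities supports that, since each later pre-dose sample is due about 48 h after the previous dose.

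**Which hours carry a concentration.** With 08:00 dosing (assumed), the protocol's night of 22:00 to 07:00 is 14 to 23 h after dosing. The 12 h sample falls at 20:00 and the 24 h sample at 08:00, so no scheduled sample falls at night. The elderly half-life comes from Protocol 3.2, where the geometric mean "was 5.46 and 4.10 hours in elderly and young subjects, respectively". Taking a simple log-linear decline from a 2 h peak, concentration relative to peak is 2^(−10/5.46) = 0.28 at 12 h, 2^(−12/5.46) = 0.22 at 14 h and 2^(−21/5.46) = 0.07 at 23 h. Filling in the night would add many low-concentration points exactly where SBP is low.

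**Simulation with zero drug effect.** From the documents: 30 subjects, 3 periods, half-life 5.46 h, tmax 2 h (within the stated 1.5 to 2.5 h). Assumed: 08:00 dosing; between-subject SD 12, period SD 4 and hourly SD 6 mmHg; exposure log-SD 0.35; day-night swing 0 to 20 mmHg, either as a night dip or as a cosine peaking at 11:00, 15:00 or 18:00. There were 200 replicates per setting. The entries are the mean SBP gap (mmHg) between the top and bottom concentration quartiles for a 10 mmHg swing; the true value is 0.

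| Rhythm | Scheduled samples: raw | change from baseline | placebo-subtracted | All 24 h: raw | change from baseline | placebo-subtracted |
|---|---|---|---|---|---|---|
| Night dip | −0.13 | −0.04 | 0.03 | 7.85 | 7.92 | −0.07 |
| Peak 11:00 | 2.64 | 2.93 | 0.01 | 3.95 | 4.21 | −0.03 |
| Peak 15:00 | 0.51 | 0.65 | −0.08 | 6.26 | 6.38 | −0.05 |
| Peak 18:00 | −1.40 | −1.50 | 0.07 | 3.83 | 3.77 | 0.02 |

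Over swings of 5 to 20 mmHg the raw gap ran from −3.0 to +5.8 with scheduled samples and from +1.7 to +15.9 with all 24 hours. With no swing there was no association. The placebo-subtracted gap stayed within 0.3 in every setting.

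**The same question as a slope.** A second simulation used scheduled samples and a 10 mmHg swing, again with no drug effect. The raw slope from zero to the mean 200 mg Cmax was −0.8 to +2.9 mmHg. After placebo subtraction it was within 0.25 of zero, and the between-trial SD of the slope fell from about 3.1 to 1.7. With all 24 hours the raw slope was about +2 to +8 mmHg; the top is the night dip, where 7.7 and 8.7 came out under slightly different variance assumptions.

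**With a real effect.** For a true effect of 5 mmHg at the mean 200 mg Cmax and scheduled samples, the raw slope averaged 3.7 to 7.3 mmHg depending on when SBP peaks. The placebo-subtracted slope averaged 5.0 to 5.2.

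**Where the precision comes from.** In the 24-hour night-dip case, baseline subtraction left the gap at 7.9 but raised the correlation from 0.17 to 0.29. It therefore removes spread between subjects but not bias. Removing the bias needs the placebo day.

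**Peak plot.** The correlation of peak hourly SBP with Cmax, or with the concentration in the peak hour, was −0.02 to 0.03 in every setting.

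**The case against.** The strongest reply has four parts.

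First, sampling. A reader might infer that a night-time fall in SBP makes an inert drug look strongly pressor: simulated night dips of 5, 10 and 15 mmHg gave false rises of about 4.0, 7.7 and 11.8 mmHg. Those figures pair SBP with concentrations at all 24 hours. The trial takes no sample between 12 and 24 h, and neither document plans to interpolate. With scheduled samples a pure night dip gives about 0. This objection stands and sets the size of the point. It does not remove the point, because a daytime rhythm still leaves a bias.

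Second, the peak plot. A reader might infer that it is confounded too, since the peak can fall in any hour. It is one value per subject and period, taken over the same 24 hours each time, so clock time is not tied to exposure. No artefact appeared. What remains is that the SAP text does not say which concentration is paired with the peak.

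Third, consequence. The plots are exploratory, and Protocol 10.3.4 leaves room for other graphs and models. An early transient effect is not left to these plots: the hourly repeated-measures model in SAP 9.4.2 compares each dose with placebo hour by hour. This stands and keeps the point minor.

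Fourth, plotting observed response against concentration is a conventional first look, and the separate figure shells, which were not available, may add detail. That is fair, but the SAP text is explicit about the plotted variables, and a better one costs nothing to collect.

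**Conclusion.** The point holds as a minor, inexpensive improvement to an exploratory analysis. Morning dosing ties concentration to the clock, and the specified hourly plot has no correction for it. With the scheduled samples and an assumed 10 mmHg swing, the bias is about −1 to +3 mmHg on a scale where the design treats 5 mmHg as a plausible true effect. Its sign depends on when SBP peaks. The larger range of about +2 to +8 mmHg applies only if overnight concentrations are filled in.

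The size rests on assumptions that the documents do not supply: the shape and depth of the daily rhythm, the 08:00 dosing time and the variance components other than the documents' 6.0 mmHg. The direction of the remedy does not depend on them, because a time-matched placebo difference cancels any rhythm common to the two days.

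Two further inferences are not supported. Using uncorrected values is not the whole cause, so switching to change from baseline would not be enough. And nothing here weakens the primary noninferiority test, the hourly repeated-measures analysis or the sample size.

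**What to change.** In SAP section 9.4.2 and the figure shells:

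1. For the hourly plot, use each subject's change from baseline in hourly mean SBP on the active day minus the change at the same clock hour on that subject's placebo day. Plot it against the lasmiditan concentration sampled in that hour.
2. State the matching rule. Counting a sample taken on the hour with the hour it ends, the 11 samples from 0.5 to 24 h fall in only 8 of the 24 hourly intervals (hours 1, 2, 3, 4, 6, 8, 12 and 24), and the first three hours hold two samples each. Say which sample is used there, and that overnight concentrations are not interpolated.
3. For the peak plot, use placebo-subtracted peak change against Cmax. This names the exposure and removes spread between subjects; it is not a time-of-day correction.
4. Keep the uncorrected plots as supporting figures if wanted.

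The cost is a few lines of SAP text and a changed variable in the figure shells, with no new data. Subjects without a usable placebo period drop out of these exploratory figures only. With up to 36 enrolled to obtain 30 completers, that is at most 36 − 30 = 6 subjects if the completion target is met.

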### **5.4. Scientific Rationale for Study Design**

A randomized, subject- and investigator-blind, placebo-controlled design is being used to minimize bias on the safety and tolerability objective. A crossover design improves the sensitivity for detecting any safety/tolerability signals in elderly subjects, particularly in relation to vital signs (as described in Section 5.1).

The washout period of approximately 48 h between each dose is adequate based on the half-life of lasmiditan.

The nonclinical and clinical data enable conducting clinical pharmacology studies in elderly healthy subjects. The single-dose design of this study limits exposure of subjects to lasmiditan and is appropriate to address the study objectives.

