## 9.4 Cardiovascular Assessment

### 9.4.1 Cardiovascular Analysis

The primary parameter for the cardiovascular analyses will be peak hourly mean values of SBP, and will be determined using ambulatory blood pressure monitoring (ABPM). For each subject, the mean SBP value will be calculated for each hour within the dosing period. The highest mean value across the 24 calculated means will be considered the peak hourly mean value. Baseline value will be defined as the mean value during the 2 hours pre-dose for each period.

Additional analysis will be performed if warranted upon review of the data.

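### The hourly SBP model cannot be fitted as coded, and its natural repair leaves no term for a subject's own repeatable hourly pattern, so the hourly confidence limits can be too wide

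*SAP*

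**What the plan says.** Besides the primary analysis of the peak, both documents plan a repeated measures analysis of the 24 hourly mean changes in SBP, tested for noninferiority at each hour (Protocol 10.3.3.2; SAP 9.4.2). Apart from the baseline covariate, the model terms are "fixed effects for time point, treatment, period, treatment sequence, and the treatment by time point interaction, and a random effect for subject".

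The SAP adds "An unstructured covariance structure will be applied" but does not say over which unit. The example code does: "repeated time / type=un subject=subject", together with "random subject". There is a fallback: "If the model fails to converge, alternative structures shall be examined using Akaike's criteria". It names neither a block nor a subject-by-hour term.

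Baseline is a single number per period: "Baseline value will be defined as the mean value during the 2 hours pre-dose for each period". Noninferiority at an hour is read from the upper 95% limit being below 10 mmHg.

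**The concern.** The Protocol justifies the design in section 5.4 by stating "A crossover design improves the sensitivity for detecting any safety/tolerability signals in elderly subjects". That gain comes from comparing each subject with himself or herself. For an hourly comparison, the natural pairing is the same subject at the same hour in another period.

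Conditions favour a personal daily pattern that repeats: one confined stay, fasted morning dosing on Days 1, 3 and 5, and subjects asked to keep to their routine on recording days. If one subject's pressure regularly rises more than average at hour 2, that feature drops out of the lasmiditan-placebo difference at hour 2. A model without a term for it counts it as noise. One baseline per period cannot remove something that differs by hour.

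The hour-by-hour results matter because the earlier study in elderly subjects saw its rise between 60 and 90 minutes. The primary peak may fall at any of 24 hours, scheduled supine vital signs after dosing are at 4 and 24 hours, and the safety analyses are descriptive. The hourly model is therefore the only planned inference tied to that window.

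**Working it through.** **Inputs from the documents.** 30 completers, SD 6.0 mmHg, margin 10, true difference 5, one-sided 0.05 (SAP 7); 24 hourly means in each of 3 periods, so 72 rows per completer (SAP 9.4.1); model terms and code (SAP 9.4.2).

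**The plan's own figure.** It concerns the primary test only. Reading 6.0 as the per-period SD, SE = 6 × √(2/30) = 1.549 and power = Φ(5/1.549 − 1.645) = Φ(1.583) = 94.3%. If 6.0 is the SD of the paired difference, power is 99.8%. The stated minimum of 90% reproduces either way. No figure is given for the hourly model.

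**The code as printed.** Let U be the 24 × 24 unstructured matrix over hours and J the 24 × 24 matrix of ones. With subject as the block and hour as the only index, each hour occurs three times in a block and all three occurrences share the same row of U. The residual matrix is R = J₃ ⊗ U, where J₃ is the 3 × 3 matrix of ones.

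- Rank of R = 1 × 24 = 24, in a 72 × 72 matrix. Same-hour residuals in different periods have correlation 1.
- With the random intercept (variance s): V = J₃ ⊗ (U + sJ), still rank 24.
- With a subject-by-time effect (variance t) also added: V = J₃ ⊗ (U + sJ + tI), still rank 24.

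V has no inverse, so the likelihood cannot be evaluated. A numerical check gave rank 24 in all three cases.

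**The natural repair.** Block by subject and period. The fitted form is V = I₃ ⊗ R + J₃ ⊗ sJ, where R is now 24 × 24. Suppose the true covariance is I₃ ⊗ E + J₃ ⊗ C, where E is within-period error and C holds the subject intercept plus a stable subject-by-hour pattern. The same-hour treatment difference has variance proportional to E at that hour, because C cancels. The model can assign only a constant part of C to the intercept; the rest goes into R. The SE ratio at hour h is √(R_hh/E_hh). If the intercept absorbs none of the pattern, this is √(1 + τ²/σ²), with pattern SD τ and error variance σ².

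**Size, with assumed variances.** The documents give neither τ nor an hourly error variance. I took σ = 6.0 by analogy with SAP 7, and subject-intercept variances of 10 and 36. I computed the large-sample maximum likelihood fit for a pattern independent from hour to hour and for a smooth one (correlation 0.9 between adjacent hours).

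| τ (mmHg) | √(1 + τ²/36) | Fitted SE excess: lowest hour, smooth pattern, to mean over hours, independent pattern |
|---|---|---|
| 0 | 1.00 | none |
| 3 | √(45/36) = 1.12 | about 5% to 11% |
| 5 | √(61/36) = 1.30 | about 13% to 29% |
| 7 | √(85/36) = 1.54 | about 23% to 52% |

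If the stable pattern lies only in the night hours (pattern variance 9 to 36), the ratio is about 1.05 to 1.40 at night but 0.995 to 1.05 in the daytime hours, which include those just after dosing.

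**Effect on the hourly rule.** With correct SEs the 95% half-width is 1.96 × 1.549 = 3.04 mmHg. At full, unabsorbed inflation f it is 3.04 × f: 3.39, 3.95 and 4.67 for τ = 3, 5 and 7. The estimate itself still varies with SD 1.549. The chance that the upper limit is below 10 when the true difference is 5 is therefore Φ((5 − half-width)/1.549):

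- correct SE: Φ(1.27) = 0.90
- τ = 3: Φ(1.04) = 0.85
- τ = 5: Φ(0.68) = 0.75
- τ = 7: Φ(0.22) = 0.59

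These are upper bounds on the loss for each τ.

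**The case against.** The strongest reply is that this is a conditional loss of efficiency in a supplementary analysis, and that it errs on the safe side. Wider limits make a false claim of hourly noninferiority less likely. The plan has no test of whether an hourly difference exceeds zero. Hourly means and changes are also summarised and plotted by treatment, so an early rise would remain visible. All of that stands, and it limits the weight of the point.

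A reader might infer that the periods are linked only through one constant subject effect however the residual block is written, and that the hourly limits will therefore be too wide. The documents do not support this. The prose names no block. The printed code ties the periods too tightly, so its defect is singularity. A period-by-time structure within subject would carry the same-hour link without a new random term. Even with subject-period blocking, the excess depends on a variance that neither document gives, and it can be negligible at 60 to 90 minutes.

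The convergence fallback does not answer the point. It leaves the block unspecified and offers no subject-by-hour term, so correcting the block alone leads straight to the model with the precision loss.

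**Conclusion.** The point holds in two parts. First, without any assumption: the hourly model as coded has a singular covariance matrix and cannot be fitted. Second, conditionally: once the residual block is corrected to subject by period, the stated terms count any stable personal hourly pattern as error and widen the hourly limits.

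The size of the second part rests on assumed variances. It is nil without a pattern and smaller when the pattern is smooth. The upper figures in the table need a pattern that changes freely from hour to hour.

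A reader might also infer that the trial's main conclusion is at risk, or that a real early rise would be hidden. Neither follows. The primary model has one value per period and a subject effect, so it pairs periods properly, and in the hourly model the point estimates are essentially unchanged. What is lost is precision in the one inferential analysis aimed at the hours of interest. A cheap correction is worthwhile, but this is not a flaw in the primary test.

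**What to change.** In SAP 9.4.2, replace the joint 24-hour model by the primary mixed model fitted separately at each post-dose hour: baseline, treatment, period, sequence, random subject, Kenward-Roger degrees of freedom. This pairs each subject's periods at the same hour and removes both the 24 × 24 matrix and the convergence fallback. Its limits are correct whether or not a stable pattern exists. Because the Protocol specifies a repeated measures model, declare the change in SAP section 11, which at present reports none.

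If a joint model is preferred, change the residual block to `subject*period` and also add a subject-by-time random effect, or use a period-by-time structure within subject. Name the order of fallback structures. Adding `subject*time` to the printed code without changing the block does not work, as the rank calculation shows. The joint model is not strictly equivalent to separate fits: it holds the baseline, period and sequence effects constant over hours, and a single subject-by-time variance assumes the pattern is equally strong at every hour.

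The cost is revised SAP wording, a few lines of code and the section 11 entry, with no new data. The small downside is that separate hourly fits do not borrow information across hours when an hourly value is missing.

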A repeated measures analysis will also be conducted in which changes from baseline in hourly mean values of SBP will be analyzed to test whether each dose of lasmiditan (100 mg, 200 mg) is noninferior to placebo at each time point (hour), assuming a noninferiority margin of 10 mmHg. A repeated measures linear mixed-effects model with baseline as a covariate, fixed effects for time point, treatment, period, treatment sequence, and the treatment by time point interaction, and a random effect for subject will be used to conduct the tests at a 1-sided significance level of 0.05. At each time point, LS means and treatment differences (lasmiditan 200 mg – placebo, lasmiditan 100 mg – placebo) will be calculated and presented with their corresponding 95% CIs, from which noninferiority of lasmiditan (100 mg, 200 mg) to placebo will be determined if the upper confidence limit is less than 10 mmHg.

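### Does reading hourly noninferiority from a 95% confidence limit contradict the one-sided 0.05 level set for the same tests?

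*SAP*

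**What the plan says.** The hourly repeated-measures paragraph in SAP section 9.4.2 contains two statements about one decision. The first fixes the level: "a random effect for subject will be used to conduct the tests at a 1-sided significance level of 0.05". The second fixes how the verdict is read, from the "corresponding 95% CIs, from which non-inferiority of lasmiditan (100 mg, 200 mg) to placebo will be determined", with the upper limit compared with 10 mmHg. Protocol section 10.3.3.2 carries the same rule: noninferiority "will be determined if the upper confidence limit is less than 10 mmHg". Neither paragraph gives the sidedness of the interval.

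The SAP adds example code for this analysis: "lsmeans trtmnt*time / alpha=0.05 cl pdiff=controll('reftrt". The protocol has no code. SAP section 3 states that the SAP takes precedence over the protocol's statistical section.

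The primary analysis works differently. Its code tests directly against the margin ("lsestimate trtmnt 'Ltn100 - Placebo' 1 0 -1 / lower testvalue=10 cl alpha=0.05"), and its gatekeeping rule uses the p-value: "If the p-value for this test is less than 0.05, then there is significant evidence that lasmiditan 100 mg is non-inferior to placebo". The primary treatment differences "will be calculated and presented with their corresponding 95% confidence intervals (CIs", but those intervals decide nothing.

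**The concern.** An unqualified 95% CI is normally taken as two-sided, and here the same phrase also covers the least squares means, which carry no one-sided hypothesis. The upper limit of a two-sided 95% interval is a one-sided 0.025 test, so on that reading the paragraph names one level and applies another.

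Unlike the primary code, the hourly code contains no test against 10, so the confidence limit alone settles each comparison. There are 24 hours and 2 doses, hence up to 24 × 2 = 48 such calls. The hourly profile is also the analysis that would show when pressure rises, which matters because the earlier study in elderly subjects saw a transient increase at 60 to 90 minutes. Two programmers could report different hours as noninferior from the same data, each citing the SAP. In the primary analysis, a reader might likewise see a dose declared noninferior beside an interval that crosses 10 mmHg.

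**Working it through.** **Inputs.** Margin 10 mmHg and one-sided alpha 0.05 (SAP section 9.4.2). SD 6.0 mmHg for the within-subject change, true difference 5 mmHg, 30 completers and up to 36 enrolled (SAP section 7, protocol section 10.1). The documents give no SD for hourly means, so using 6.0 for the hourly bands below is an assumption. It is taken two ways: as the SD of one period's change, or as the SD of the paired difference between two periods.

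**The plan's own figure.** At n = 30 the distance to the margin is 10 − 5 = 5 mmHg.
- Per-period SD: SE = 6 × √(2/30) = 1.549, with 90 − 30 − 2 − 2 = 56 df (observations less subjects, treatments and periods). Noncentral-t power at one-sided 0.05 is 93.9%.
- Paired-difference SD: SE = 6/√30 = 1.095, 29 df. Power is 99.8%.

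Both meet the stated 90% or more.

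**Level implied by each interval.** The upper limit of a two-sided 95% interval uses z = 1.960, a one-sided error of 0.025. A one-sided 95% bound, which is also the upper limit of a two-sided 90% interval, uses z = 1.645, a one-sided error of 0.05. Only the second matches the stated level.

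**Where the readings disagree.** The largest estimate that passes is 10 − t × SE.

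| n | SD 6.0 taken as | SE | df | t(0.95) | t(0.975) | One-sided 95% bound | Two-sided 95% limit |
|---|---|---|---|---|---|---|---|
| 30 | per period | 1.549 | 56 | 1.6725 | 2.0032 | 7.41 | 6.90 |
| 30 | paired difference | 1.095 | 29 | 1.6991 | 2.0452 | 8.14 | 7.76 |
| 36 | per period | 1.414 | 68 | 1.6676 | 1.9955 | 7.64 | 7.18 |
| 36 | paired difference | 1.000 | 35 | 1.6896 | 2.0301 | 8.31 | 7.97 |

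The band width is (t(0.975) − t(0.95)) × SE. At n = 30, for an assumed SD of 4, 8 or 12 mmHg, it is 0.34, 0.68 or 1.02 mmHg (per period) and 0.25, 0.51 or 0.76 mmHg (paired).

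**Chance of disagreement per comparison** (n = 30, SD 6.0, noncentral t; probability of a noninferiority call under the 0.05 rule, then under the two-sided 95% rule).
- True difference 5 mmHg: 0.939 and 0.887 per period, a gap of 5.1 points; 0.9975 and 0.9928 paired, a gap of 0.5 points.
- Largest gap: 12.9 points near 7.1 mmHg (per period) and 13.2 points near 7.9 mmHg (paired).
- True difference 10 mmHg: 0.050 and 0.025 either way. The two-sided reading lowers the error rate.

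**Which reading the SAP supports.** The paragraph states one-sided 0.05. The code beneath it uses `alpha=0.05` with `controll`, the lower one-tailed form of the comparison with control. The limit this gives for lasmiditan minus placebo is a one-sided 95% upper bound, so run as coded the rule is a one-sided 0.05 test. That is also the only reading under which the paragraph's two statements agree. The primary code likewise puts `lower` and `cl alpha=0.05` in one statement, so nothing establishes that the displayed primary interval is two-sided.

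**The case for a change.** The strongest case for a change is that the code is offered only as an example, that sidedness hangs on the last letter of an option the SAP never explains, and that the protocol has no code. A decision rule should be readable from the prose, and one added phrase would cost nothing.

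Part of this stands. The prose is incomplete, and naming the bound as one-sided would be tidier. The rest carries less weight. The protocol's silence matters little because the SAP takes precedence. The absence of a coded test against 10 is no defect, since comparing a confidence limit with 10 is equivalent to testing against 10 at the matching level. The count of 48 calls overstates the exposure: protocol section 3.2 describes a rise that was maximal at about 1.5 hours and had moved back toward baseline by 3 hours, so few hours should lie near the margin. The 13-point gap is a maximum at the least favourable true difference.

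**Conclusion.** The two statements can be read together without conflict, and the SAP's code points to the reading that reconciles them: a one-sided 95% upper bound at one-sided 0.05. What remains is missing detail in the prose. It does not call for a change to the plan.

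The consequence of the other reading is small and runs in the cautious direction. It would halve the per-comparison error from 5% to 2.5% in a supportive analysis and could alter an hourly call only for estimates in a band about 0.4 to 0.5 mmHg wide at n = 30 and SD 6.0. The primary decision, its error rate and its planned power are untouched, because they rest on the gatekept p-value against 10 mmHg.

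This conclusion rests on the usual meaning of the one-tailed SAS option, which the SAP names but does not define. The band widths rest on an SD borrowed from the primary sizing and on simple crossover or paired formulas in place of the planned unstructured repeated-measures model. A different hourly SD would rescale the band but would not change its direction or reach the primary result.
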